At 3 months after delivery, all subjects will be contacted by phone, text, or email to complete a questionnaire to determine whether they have had a known expulsion, pregnancy, or elective IUD removal. The questionnaire will include questions regarding ease of placement and overall satisfaction with the timing of placement. Subjects will be compensated for their participation in the study after the 3 month contact.

4. Subject Recruitment: Participants will be recruited upon admission to OHSU Labor and Delivery. Researchers will pre-screen eligible subjects based on eligibility criteria through EPIC medical records and collect demographic information from women who elect to enroll in the study. Women who desire an IUD and have a history of poor

prenatal clinic attendance with income <300% of the federal poverty line will be approached by residents. Subjects will be selected for the study according to the selection criteria detailed below.

5. Consent: Whenever feasible the information about this research project will be made available to patients prior to labor. Due to the nature of the study consent may be obtained during labor or in the immediate postpartum period. In order to ensure adequate consent is obtained in patients who present in labor, patients will be asked if it is an appropriate time to discuss a research study regarding timing of IUD placement. If the time is not appropriate the investigator will wait until the circumstances have changed to re-visit the research study. Whenever possible research investigators will discuss the proposed research and obtain informed consent in the presence of one of the patient's independent labor support persons. Patients will not be approached for participation in the study until at least 1 hour has passed after administration of systemic opioids or sedative medications. If feasible it may be preferable to delay approaching a patient until after epidural placement if such analgesia is desired by the patient as studies have shown that epidural analgesia does not alter mental status. Consent will always be obtained in the patient's primary language.

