It is important to emphasize that consent prior to admission on labor and delivery is not possible, as we are seeking to enroll a group of women who have poor attendance at prenatal clinics. While there are many reasonable concerns around obtaining consent in labor, the investigators in this study will be physicians who are experienced with the consent process for medical and surgical procedures (including the placement of IUDs immediate postplacental). These physicians routinely obtain consent on the L&D unit, and understand the dynamics and unique challenges of laboring women. We have built in additional flexibility to have potential subjects complete the informed consent process after delivery.

- **6. Study Duration:** The total duration for the study for each participant is expected to be approximately 3 months.
- **7. Number of Subjects and Statistical Power:** The study is expected to enroll 50 female subjects. With the proposed sample size of 20 subjects in each group, the study will have power of 81% to yield a statistically significant result. This computation assumes that a 40% difference in the primary outcome of proportion of subjects using an IUD at 3 months of follow-up (corresponding to proportions of 0.9 versus 0.5). This effect size is estimated assuming 90% IUD continuation rate in the immediate IUD group which takes into account the high expulsion rate, as compared to a 50% IUD continuation rate in the delayed IUD group which corresponds to the rate of return seen in this population as supported in two prior studies conducted at OHSU^{8,9}.

8. Selection of Subjects:

- a. Inclusion criteria:
 - i. Female
 - ii. 18 yo or older
- iii. Singleton pregnancy at ≥ 32 weeks gestation at time of enrollment

- iv. Voluntarily requesting either copper T380A or levonorgestrel IUD placement for postpartum contraception
- v. English or Spanish speaking
- vi. Able to give consent and agree to the terms of the study
- vii. Less than 10 prenatal visits or 2 or more no show visits
- viii. Since IUDs are not on our hospital formulary, the patient must qualify for a LARC IUD (this includes all Oregon Health Plan (OHP) or Citizen/Alien Waived Emergent Medical (CAWEM) insured patients or women with income <300% of the federal poverty line).

b. Exclusion Criteria:

- i. Anatomic uterine abnormalities that prevent proper fundal placement of IUD (obstructive myomata, bicornuate, septate, etc)

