- ii. Chorioamnionitis (also consider other risk factors such as prolonged rupture of membranes >18 hours, prolonged labor >24 hours, fever >38C)
- iii. Puerperal sepsis
- iv. Unresolved postpartum hemorrhage
- v. Extensive genital trauma
- vi. Current incarceration
- vii. Known or suspected untreated endocervical gonorrhea, chlamydia
- viii. Wilson's disease, copper allergy (Paragard only)
- ix. Known or suspected cervical or endometrial cancer or pelvic tuberculosis
- x. Current breast cancer (LNG-IUS only)
- xi. SLE with severe thrombocytopenia (Paragard only)
- xii. Trophoblastic disease (benign or malignant)
- xiii. AIDS not stable on antiretroviral
- **9. Treatment Allocation:** Randomization will be accomplished by opening the next in a series of numbered sealed opaque envelopes. The envelope will contain the subject randomization assignment. The envelope will be opened immediately after delivery. The randomization scheme will be by computer block randomization.
- **10. Study Medications:** All of the study medications are FDA-approved and they will be used according to the labeling indications.
- a. The **levonorgestrel intrauterine system (Mirena® IUS)** is a radio-opaque T-shaped polyethylene device containing 52mg of levonorgestrel dispersed in polydimethylsiloxane on its stem. The progestin is released at a rate of 15 mcg per day. It is FDA approved for up to five years of use in the United States.
- b. The Copper T380A IUD (ParaGard®) is a T-shaped polyethylene device with 380 mm² of exposed surface area of fine copper wire wound around its arms and stem. Barium sulfate has been added to the polyethylene frame to make the device radio-opaque. A 3-mm plastic ball is located at the base of the IUD, through which the polyethylene monofilament string passes. It is FDA approved for up to 10 years of use in the United States.

11. Study Laboratory Tests and Procedures:

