 - ii. Schedule follow up appointment if needed
- c. IUD placement(IUD insertion postplacental or postpartum visit): Prior to IUD insertion, the provider will discuss informed consent with the patient and will sign a formal surgical consent form to be placed in the patient's medical chart. The IUD will be inserted as detailed in study procedures. Subjects receiving postplacental IUDs will be encouraged to have the IUD strings checked at their postpartum visit by their primary provider. All subjects will be counseled on how to check their IUD strings.
 - i. IUD insertion procedure
- d. Follow Up: At three months postpartum, participants will be contact by phone, text, or email. They will be asked whether they have had a known expulsion, pregnancy, or elective IUD removal. A brief questionnaire will include questions regarding ease of placement and overall satisfaction with the timing of placement. A study stipend will be provided at this time. Participants who did not follow up for IUD insertion or those that report IUD expulsion will be encouraged to contact their primary provider to discuss contraception. Chart review for confirmation of IUD placement will be performed.
 - i. Final questionnaire
 - ii. Study subject stipend paperwork
- **13. Data Analysis:** Data will be validated and entered into a computer. Statistical analysis will be carried out using STATA. Principal outcome measures include pregnancy and removal rates, cumulative expulsion, and continuation rates.
- 14. Data management: All patient data sheets will be kept confidential and in a locked office. A unique patient study identification number will be placed on the data forms. Study identification will be subject last initial and a unique three digit identifier. No subject names will be included with the study data. Study identifiers kept in a logbook will be assigned to each patient to protect confidentiality. For subjects who do not enroll, all screening documents will be kept in a locked office and password protected computer and confidentially destroyed once study is complete. When undergoing statistical analysis, the forms will be transferred to the primary investigator's locked office. Patient identifiers will be stored separately from the data files on the primary investigator's password-protected computer. Only the study investigators will have access to this identifier list.

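### The 3-month follow-up has no stated way to record an IUD removal initiated by a clinician, although removal and continuation rates and IUD use at 3 months are outcomes

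*Combined protocol and SAP*

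**What the plan says.** Section 3 (Study Design) has every subject contacted at 3 months to "complete a questionnaire to determine whether they have had a known expulsion, pregnancy, or elective IUD removal". Section 12.d (Follow Up) repeats the same list: "They will be asked whether they have had a known expulsion, pregnancy, or elective IUD removal". The other content named for that contact concerns the experience of placement: "A brief questionnaire will include questions regarding ease of placement and overall satisfaction with the timing of placement". The chart review in Section 12.d has one stated purpose: "Chart review for confirmation of IUD placement will be performed".

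The outcomes are wider than these questions. Section 7 gives the primary outcome as the "proportion of subjects using an IUD at 3 months of follow-up". Section 13 (Data Analysis) states: "Principal outcome measures include pregnancy and removal rates, cumulative expulsion, and continuation rates". There the removal rate is not limited to elective removals.

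Nothing elsewhere fills the gap. Section 16 records why a subject leaves the trial, not why a device was taken out. Section 12.c encourages a string check at the postpartum visit for postplacental devices but does not list its result as data. No section gives a direct question on whether a device is in place at 3 months, or a rule for deriving 3-month use from questionnaire and chart.

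**The concern.** Consider a woman whose clinician decided to remove the device because of infection, malposition or perforation, and who had no replacement. She has had no expulsion and no pregnancy, and she may reasonably not call the removal elective. She can truthfully answer no to all three items. Chart review for placement then confirms that she received a device. Nothing in the plan as written brings the removal to light.

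Two results are exposed. The removal rate in Section 13 would leave out clinician-initiated removals. The primary outcome could count a woman without a device as a user, depending on how use is derived. This differs from an unnoticed expulsion: the woman and her clinician both know that the device is out, so the gap lies in the wording of the question and can be closed by changing it.

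**Working it through.** **1. Match each way a device can cease to be in use with its stated source.**

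| Event by 3 months | Stated source |
|---|---|
| Never placed | Chart review (Section 12.d) |
| Known expulsion | Questionnaire (Sections 3, 12.d) |
| Elective removal | Questionnaire (Sections 3, 12.d) |
| Clinician-initiated removal | None stated |

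The last row belongs in the removal rate and in non-use, but has no stated source.

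**2. Reproduce the plan's own figure.** Section 7 gives 20 per arm, 0.9 versus 0.5, and 81% power. Alpha and sidedness are not stated; I take 0.05 two-sided. With the pooled-variance normal approximation:

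- Mean proportion = (0.9 + 0.5)/2 = 0.7.
- SE under the null = √(2 × 0.7 × 0.3/20) = 0.1449.
- SE under the alternative = √((0.09 + 0.25)/20) = 0.1304.
- z = (0.4 − 1.96 × 0.1449)/0.1304 = 0.889, so power = 81.3%.

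The stated figure reproduces and is not in dispute.

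**3. Bias if the same share of devices is missed in both arms.** Let m be the share of apparently continuing devices that were in fact removed. The true rates are 0.9(1 − m) and 0.5(1 − m), and the true difference is 0.4(1 − m). The observed difference stays at 0.40. The documents give no rate of medical removal, so m is an assumption.

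| m | True immediate | True delayed | True difference | Power at true rates |
|---|---|---|---|---|
| 2% | 0.882 | 0.490 | 0.392 | 78.4% |
| 5% | 0.855 | 0.475 | 0.380 | 73.9% |
| 10% | 0.810 | 0.450 | 0.360 | 66.6% |

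The overstatement favours the immediate arm, because under the plan's own rates more devices are in use there. At 5% it is 0.02.

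**4. Sensitivity of the test to individual women.** One woman moves an arm by 1/20 = 5 percentage points. Section 13 names no test; I use a two-sided Fisher exact test at 20 per arm. The starting point is the planned result, 0.9 × 20 = 18 versus 0.5 × 20 = 10.

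| Hidden removals (immediate, delayed) | True table | p |
|---|---|---|
| 0, 0 | 18/20 vs 10/20 | 0.014 |
| 1, 0 | 17/20 vs 10/20 | 0.041 |
| 2, 0 | 16/20 vs 10/20 | 0.096 |
| 1, 1 | 17/20 vs 9/20 | 0.019 |
| 2, 1 | 16/20 vs 9/20 | 0.048 |

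The 2, 1 row is roughly in proportion to the devices in use (18 to 10). Of these rows, p exceeds 0.05 only when two removals are hidden in the immediate arm and none in the delayed arm.

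**The case against.** Several points on the other side stand.

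- **The form is not in the documents.** Its described content need not be exhaustive, and a participant or chart reviewer might mention a removal unprompted. The supportable statement is that no capture is stated, not that such removals will be missed. Even so, a principal outcome should not depend on incidental reporting.
- **Elective is undefined.** It may only be meant to separate deliberate removal from expulsion, and a removal that a woman requests for pain or bleeding could naturally be called elective. The clear gap is therefore removal initiated by a clinician.
- **Counting a removed device as in use is an inference.** It needs a derivation of placement minus the three listed events. No section states that derivation, and none rules it out.
- **The effect on significance depends on where the hidden removals fall.** Putting all of them in the immediate arm gives the most adverse figures; a roughly proportional split leaves p just below 0.05.

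A reader might also infer that a safety follow-up has failed, or that the trial is defective because it cannot compare the safety of the two timings. The documents do not support this. They never describe the 3-month contact as a safety contact, the objective in Section 2 is uptake, and Section 13 lists no safety comparison. The infection-related exclusions in Section 8.b, such as "Known or suspected untreated endocervical gonorrhea, chlamydia", govern eligibility. The testing in Section 11.a is tied to office placement under clinic protocols. Neither shows a fault in outcome follow-up. Wanting complication data is reasonable, but it is mainly a preference about scope.

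**Conclusion.** The point holds for how removal is ascertained. The planned questions and chart review are narrower than the outcomes they serve, and a clinician-initiated removal has no stated route into the removal rate, the continuation rate or the primary outcome. This follows directly from the text of Sections 3, 7, 12.d and 13.

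The effect on the primary comparison is conditional. It requires that such removals occur, that they are not volunteered or noticed, and that use is derived as confirmed placement minus the listed events. Under an equal per-device miss rate the bias is modest and favours the immediate arm (0.02 at an assumed 5%). With 20 per arm, one or two women can still move the p-value from 0.014 to between 0.019 and 0.096, depending on their number and arm. A reader might infer from the upper end that the trial's conclusion would be overturned; that needs two hidden removals, both in the immediate arm, for which the documents give no basis. The change should be made because it is cheap and removes the doubt.

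**What to change.** 1. In Sections 3 and 12.d, add a direct question, *Is an IUD in place now?*, and replace the elective-removal item with *any IUD removal (date, reason)*.
2. In Section 12.d, extend the planned chart review from placement to placement and removal, where records are accessible, by the same procedure in both arms. The equal procedure matters because Section 11.c leaves most delayed placements to usual-care providers, and uneven access to records could itself bias the comparison.
3. In Section 13, define 3-month use as a device in place. Count any removal or expulsion without replacement as non-use, and state which source prevails when questionnaire and chart disagree.
4. In Section 13, tabulate removals by reason and arm.

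A short complication item (infection, perforation, readmission) at the same contact is a low-cost optional addition.

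**Cost.** A wording amendment to Sections 3, 12.d and 13, a slightly longer contact, and some work to obtain outside records. The release in Section 12.a is described in terms of contact information, so check whether it also covers those records. Measured continuation may come out slightly lower. The stated sample size does not need to change.

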Both the levonorgestrel and copper IUD provide contraception without interfering with breastfeeding.⁵ For women with limited access to medical care, hospitalization for delivery provides a unique opportunity to address the need for contraception. The major disadvantage to postplacental placement is an increase in expulsion rates; as high as 8-24% by 6 months. One study suggests that the rate of expulsion has to do with the insertion technique and provider experience.^{6,7} Despite this higher expulsion rate, continuation rates for IUD use at 6 months appear to be equivalent for postplacental IUD as compared to routine 6 week insertion. In a setting where women typically attend a postpartum follow-up visit where IUDs are routinely available, postplacental placement has not been shown result in higher uptake of IUDs or to be cost-efficient.⁶ However, in a population at high risk for lack of postpartum follow-up, the higher expulsion risk becomes less a concern, as the alternative to postplacental placement would be nonuse of contraception or use of a less effective method. *Identification of a group of postpartum* women at high risk for poor follow-up would enable targeted delivery of postplacental placement. Recent studies at our institution have shown women with a history of poor attendance to prenatal appointments are at high risk of not returning for routine postpartum IUD placement. 8,9 Based on these recent studies, we hypothesize that women with less than 10 prenatal visits or 2 or more no show visits who receive an immediate postplacental IUD will have higher rates of IUD continuation at 3 months than women who are scheduled to receive an IUD at a delayed postpartum visit.

2. Study Objective: To determine whether immediate postplacental IUD placement will improve IUD uptake at 3 month postpartum in women with a history of poor prenatal clinic attendance.

3. Study Design:

The study will be a randomized clinical trial. Women with less than 10 prenatal visits and/or 2 or more no show visits who desire an IUD will be considered for enrollment. If consented and meet inclusion criteria, they will be randomized after delivery to receive an IUD immediately postplacental or at their routine postpartum visit.

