Women who plan to deliver a live birth singleton via vaginal or cesarean delivery at OHSU hospital will be considered for inclusion in the study. Women who desire an IUD for postpartum contraception will be approached for study participation. The postpartum contraception plan is routinely documented during their prenatal course. It is also addressed by the obstetrical team upon admission to Labor & Delivery at OHSU. The obstetrical team will identify subjects who present in labor who meet the criteria of poor prenatal clinic attendance and express interest in intrauterine contraception. These women will be provided with information about the study, and if interested will be provided with informed consent counseling. Completion of the informed consent process and signing of the consent can be done before or after delivery depending on the individual circumstances of the labor. Subjects that meet all inclusion and no exclusion criteria, and agree to the terms of the study, will be entered into the study after a discussion of study procedures and signing the informed consent. Immediately after vaginal or cesarean delivery, consenting subjects will be randomized to immediate postplacental IUD placement or IUD placement at their routine postpartum visit. Women randomized to the immediate postplacental IUD group will receive their IUD within 60 minutes of placental delivery. To minimize interference with the early postpartum interval, all subjects will be asked to complete a demographic questionnaire at their convenience at some point prior to hospital discharge. Prior to discharge from the hospital women who received a postplacental IUD will be assisted in scheduling a routine postpartum visit with their primary provider. Subjects who are randomized for IUD insertion at their postpartum visit will be assisted in scheduling a postpartum visit and IUD placement with their usual obstetrical care provider. All subjects in the delayed group will be provided with contact information for the Women's Health Research Unit at OHSU. If a subject cannot obtain an IUD at her usual place of care, the device will be placed at no cost through the WHRU.

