c. Office IUD insertion: All insertions will be done according to the standard operating procedure at each clinic. A variety of usual care providers will provide the device, and the placement is outside of the study procedure. An exception will be subjects unable to obtain a device through their usual clinic. These women may obtain a device through an investigator at Women's Health Research Clinic. All study investigators will undergo review of manufacturer instructions. Pain management will be per clinical judgment and includes either no treatment, 1% lidocaine gel applied directly to the cervix with a cotton swab, or 1-2 mL of 1% lidocaine injected into the cervix prior to tenaculum placement. No paracervical block will be used unless clinically indicated. Dilation will be used if necessary. The IUD will be placed following FDA approved manufacturer instructions.

12. Study Visits

a. Screening: Pregnant women with a history of poor prenatal clinic attendance and OHP or CAWEM insurance who have identified IUD as their planned form of contraception will be approached upon admission to OHSU Labor and Delivery by a study investigator. After a description of the study and confirmation of their intent for IUD, informed consent will be obtained, screening for study inclusion criteria will be performed, and the initial questionnaire will be administered if possible. Release of information will be signed including the subjects contact information so that they can be contacted at 3 months postpartum as detailed below.

- i. Subject screening
- ii. Informed Consent
- iii. Release of information

- iv. Initial Questionnaire
- vi. Privacy Practices Information
- vii. Study Stipend Paperwork
- b. Randomization: Immediately after delivery the study subject randomization will be performed using sequential opaque envelopes. The subject will be informed of her group allocation and the study procedure will be reviewed. For participants randomized to insertion at their postpartum visit, an appointment will be scheduled with their primary provider prior to hospital discharge. If they are unable to obtain an IUD from their primary clinic, they will be given information to arrange IUD insertion at the OHSU Women's Health Research Unit. While placement at the WHRU is not "real world", we feel that it this follow-up is ethically justified to provide the same option to all participants for a no cost IUD regardless of randomization group.
 - i. Randomization revealed

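### Does the absence of a rule for women not reached at 3 months bias the primary comparison of IUD use?

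*Combined protocol and SAP*

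**What the plan says.** Section 7 defines the outcome as the "primary outcome of proportion of subjects using an IUD at 3 months of follow-up", with planned proportions of 0.9 and 0.5. It also states: "The study is expected to enroll 50 female subjects. With the proposed sample size of 20 subjects in each group". The purpose of the other 10 women is not given.

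The hypothesis in Section 1 is that women given an immediate device will have "higher rates of IUD continuation at 3 months than women who are scheduled to receive an IUD at a delayed postpartum visit". The comparison is thus with women scheduled for insertion, so a delayed-arm woman who never returns counts as not using.

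The two arms generate different records. Section 3 states: "Women randomized to the immediate postplacental IUD group will receive their IUD within 60 minutes of placental delivery". For the delayed arm, Section 11c states: "A variety of usual care providers will provide the device, and the placement is outside of the study procedure". Section 12d asks every woman at 3 months, by phone, text or email, about expulsion, pregnancy and removal, and adds a chart review to confirm placement. Section 12a has a release of information signed. Section 15 pays \$50 after the 3-month call.

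Section 13 names the software and the outcomes: "Principal outcome measures include pregnancy and removal rates, cumulative expulsion, and continuation rates". Section 16 still sends women who withdraw to the 3-month questionnaire and analyses their earlier data by intention to treat. No section assigns a status to a woman who does not respond.

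**The concern.** Section 5 says of the population: "we are seeking to enroll a group of women who have poor attendance at prenatal clinics". Some women are likely to be missed at 3 months, and the 10 enrolled beyond the 40 in the power statement could be read as an allowance for that.

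For a missed woman, the records may show only whether a device was placed. In the immediate arm that is nearly always yes. In the delayed arm it is no unless an outside insertion is found. Scoring from those records would class unreached women as users in one arm and non-users in the other. It would also miss expulsions in unreached immediate-arm women, although Section 1 names as the main drawback of postplacental placement "an increase in expulsion rates; as high as 8-24% by 6 months". The primary difference could be inflated, or produced where none exists.

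**Working it through.** **Inputs.** Rates of 0.9 and 0.5, 20 per group, 81% power and 50 enrolled come from Section 7. Assumptions, because the documents give no figure: two-sided alpha of 0.05, N = 25 randomised per arm, k = 5 unreached per arm unless stated, and all unreached immediate-arm women had a device placed.

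**The plan's power.** Pooled normal approximation, mean proportion 0.7, n = 20:
- z = [0.40 − 1.96 × √(2 × 0.7 × 0.3/20)] / √[(0.9 × 0.1 + 0.5 × 0.5)/20] = (0.40 − 0.284)/0.1304 = 0.89
- Power = 81.3%, which agrees with the stated 81%.

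**Effect of the scoring rule at the planned rates** (18/20 and 10/20 using among women reached; two-sided Fisher test):

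| Unreached women scored as | Immediate | Delayed | Difference | p |
|---|---|---|---|---|
| Missing | 18/20 | 10/20 | +40 points | 0.014 |
| Not using, both arms | 18/25 | 10/25 | +32 | 0.045 |
| Using, both arms | 23/25 | 15/25 | +32 | 0.018 |
| Placement taken as use, no delayed insertion found | 23/25 | 10/25 | +52 | 0.0002 |
| Opposite extreme | 18/25 | 15/25 | +12 | 0.55 |

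All three rules that treat the arms alike lead to the same conclusion here. The last two rows are bounds that score the arms in opposite directions.

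**Size of the bias if placement were taken as use.** Let D be the true difference, with the same use rates in reached and unreached women. The scored difference is D(1 − k/N) + k/N, so the inflation is (k/N)(1 − D).
- Planned rates: (5/25) × (1 − 0.4) = 0.12, so 40 points become 52.
- No true difference: 5/25 = 0.20. For k = 1, 2 and 3 it is 4, 8 and 12 points.

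**False-positive rate under that rule.** Exact enumeration over two binomials of size 25 − k, Fisher test, true use assumed 70% in both arms:

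| Unreached per arm | Delayed insertions found in chart | Rejection rate |
|---|---|---|
| 1 | 0 | 2.6% |
| 2 | 0 | 4.2% |
| 3 | 0 | 7.3% |
| 5 | 0 | 19.8% |
| 5 | 2 | 6.7% |
| 5 | 3 | 3.6% |

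With 5 unreached per arm treated as missing, the rate is 2.5%.

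**Would a fixed complete-case rule be better?** Section 7 equates the delayed-arm rate with the rate of return, so an unreached delayed-arm woman may well be a true non-user. Suppose all 5 are, and the true rates over all 25 are 0.9 and 0.5 (12.5 expected users in the delayed arm):
- Complete case: 0.9 − 12.5/20 = 0.9 − 0.625 = +27.5 points, 12.5 below the truth.
- Placement taken as use: 23/25 − 12.5/25 = 0.92 − 0.50 = +42 points, 2 above the truth.

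Counting unreached women as not using in both arms lowers power to 63.2% by the same approximation (25 per arm, 0.72 against 0.40). Neither simple rule is best in every case.

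**The case for a change.** The strongest case for a change is that the rule is missing, the records differ by arm in a known direction, and the trial is small. With 5 unreached per arm, the p-value runs from 0.0002 to 0.55 across the possible scorings, and a sentence written in advance would cost almost nothing. Section 16 also leaves open whether data up to withdrawal may serve as 3-month status.

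The missing rule and the asymmetry stand, and so does the arithmetic. The harm does not follow from the plan, because it needs a scoring rule found nowhere in the protocol. The outcome is use at 3 months, and the only described source for loss of a device is the woman's report at that time. The chart review in Section 12d reads naturally as a check on that report. Section 16 concerns withdrawals and still seeks the questionnaire from them.

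The 19.8% is an illustration near the worst case: equal use at an assumed 70%, one woman in five unreached, and no delayed insertion traced. The documents give no non-contact rate. They do describe three contact routes, a payment tied to the 3-month call and a signed release of information. An expulsion noted at the postpartum string check encouraged in Section 12c could also reach the chart before 3 months.

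**Conclusion.** The concern does not call for a change. The protocol gives no 3-month status for women not reached, but it defines the outcome and the comparison well enough for an analyst to fill the gap by treating both arms alike and reporting missing status by arm. Under the assumed 5 unreached of 25 per arm and the planned rates, that gives 40 points with unreached women missing or 32 with them not using, both with p below 0.05.

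The 12-point inflation at the planned rates, and the 20 points under no true difference, arise only if placement is read as use and no delayed insertion is traced. The plan does not say this. With 1 or 2 unreached per arm, the Fisher rejection rate under that reading is still below 5% at the assumed 70% use. Choosing between complete case and non-use as the main analysis is a judgement that either side can defend, so prescribing one would bring no clear gain. The conclusion rests on the assumed equal split, non-contact numbers and two-sided alpha of 0.05, none of which the documents state.
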